# 10.5. Early Termination Visit

Patients who prematurely discontinue study treatment will be asked to complete an early termination visit. The following assessments will be performed:

- Blood/urine sampling for the following laboratory tests:
  - Hematology: RBC count, total and differential WBC count (basophils, eosinophils, lymphocytes, monocytes, and neutrophils), platelet count, hemoglobin, hematocrit, MCV, MCH, and MCHC
     Note: All total WBC and differential WBC counts will be blinded during the study.
  - Blood chemistry: sodium, potassium, chloride, calcium, magnesium, phosphate, blood urea nitrogen, random glucose, albumin, alkaline phosphatase, creatinine, SGPT/ALT, SGOT/AST, GGT, amylase, total bilirubin, conjugated bilirubin, hemoglobin A1c. Abnormal laboratory parameters inconsistent with clinical presentation of MS or suspicious of underlying medical condition should be repeated for accuracy. If an increase of amylase above the clinically notable value (≥ 300 U/L) is observed at any post randomization visit, lipase should be tested to determine the origin of elevated amylase (pancreatic versus extra pancreatic)
  - Urinalysis: leukocytes, specific gravity, bilirubin, blood, glucose, ketones, pH, protein, and urobilinogen
  - Urine beta-hCG (females of childbearing potential only). If the urine pregnancy test is positive, do not dose and confirm with a serum pregnancy test.
  - Coagulation panel: PT and partial thromboplastin time PTT
  - sTSH

- PK sampling
- Complete physical examination: including evaluation of heart, lung, head and neck, abdominal, neurological, skin, and extremities
- Weight
- Vital signs: body temperature, blood pressure and heart rate
- 12-lead ECG
- Review study drug accountability and compliance
- Brain MRI
- EDSS and neurological examination
- MSFC and LCLA
- MSQOL-54
- Pulmonary function tests including FEV1, FVC, and DLCO measurements
- OCT evaluation
- Dermatological examination
- Suicidality assessment using the C-SSRS
- Record concomitant therapy
- Record AEs/SAEs

# 10.6. Follow-Up

Patients will be asked to return for a follow-up visits 4 weeks after their last dose of study treatment of either Part A or Part B.

During the follow-up visit the following assessments will be performed:

- Blood/urine sampling for the following laboratory tests:
  - Hematology: RBC count, total and differential WBC count (basophils, eosinophils, lymphocytes, monocytes, and neutrophils), platelet count, hemoglobin, hematocrit, MCV, MCH, and MCHC
     Note: All total WBC and differential WBC counts will be blinded during the study.
  - Blood chemistry: sodium, potassium, chloride, calcium, magnesium, phosphate, blood urea nitrogen, random glucose, albumin, alkaline phosphatase, creatinine, SGPT/ALT, SGOT/AST, GGT, amylase, total bilirubin, conjugated bilirubin, hemoglobin A1c. Abnormal laboratory parameters inconsistent with clinical presentation of MS or suspicious of underlying medical condition should be repeated for accuracy. If an increase of amylase above the clinically notable value (≥ 300 U/L) is observed at any post randomization visit, lipase should be tested to determine the origin of elevated amylase (pancreatic versus extra pancreatic)

- Urine beta-hCG (females of childbearing potential only). If the urine pregnancy test is positive, do not dose and confirm with a serum pregnancy test.
- Vital signs: body temperature, blood pressure and heart rate
- 12-lead ECG
- Suicidality assessment using the C-SSRS
- Record previously ongoing AEs/SAEs

# 10.7. Study Stopping Rules

The Sponsor has the right to terminate the study prematurely for safety reasons. In addition, the Sponsor may terminate the study prematurely for administrative reasons at any time. In all cases all necessary measures have to be taken to guarantee appropriate safety follow-up of all patients already included in the study.

The IEC or IRB and the Regulatory Authorities will be informed in writing about any premature termination of the study.

#### 11. METHODS OF ASSESSMENT

Tests and assessments are common to Parts A and B of the study unless otherwise indicated.

The study design is shown in Figure 1. Tests and Assessments are outlined Table 1 and Table 2 (Part A), Table 3 and Table 4 (Part B), and Table 5 (cardiac monitoring during dose titration), and additional detail regarding procedure is included in Section 10.

## 11.1. Efficacy Assessments

#### 11.1.1. Magnetic Resonance Imaging (MRI)

Brain MRIs will be acquired with and without Gadolinium. The same MRI protocol will be used across all sites. To ensure quality data and standardization the same machine and software should be used throughout the study. MRIs for MS lesions will be read blinded to treatment allocation at a centralized reading facility.

In Part B and in the Blinded Extension to Part A, MRI scans should not be performed until 30 days after the last dose of methylprednisolone treatment for relapse. Previously scheduled MRIs should be rescheduled as necessary if a relapse occurs.

Total number of GdE lesions, number of new or enlarging hyperintense T2-weighted lesions, lesion volume (T2-weighted images), volume of unenhancing T1-weighted lesions and brain volume (i.e., brain atrophy) will be collected and reported.

The MRI scans will be read locally for non-MS pathology.

#### 11.1.2. Expanded Disability Status Scale (EDSS) and Neurological Examination

The EDSS is a standardized method, widely accepted, numerical scale used to evaluate disability in people with MS (Kurtzke, 1983).

The EDSS is evaluated according to signs and symptoms observed during a standard neurological examination. These clinical observations are classified in 7 FS scales, each of them grading signs and symptoms for different neurological functions: pyramidal, cerebellar, brainstem, sensory, bowel or bladder, visual, and cerebral.

The study will require the same blinded evaluator (refer to Section 9.1.2.2) should perform all EDSS assessments for an individual patient when possible. In addition, EDSS raters will be certified using the Neurostatus Standardized Examination and Assessment prior to study initiation and examiners will be re-certified every two years throughout the conduct of the study.

#### 11.1.3. Relapse Assessment

A relapse is defined as the occurrence of new or worsening neurological symptoms attributable to MS and immediately preceded by a relatively stable or improving neurological state of at least 30 days. The new or worsening neurological symptoms must be accompanied by objective neurological worsening consistent with an increase of at least half a point on the EDSS, or 2 points on one of the appropriate FS scores, or 1 point on two or more of the appropriate FS scores. The change must be documented by the blinded evaluator at either scheduled or unscheduled visits and must affect the FS scales that correspond to the patient's symptoms (e.g.,

pyramidal, gait, cerebellar, brainstem, sensory, or visual). Symptoms must persist for > 24 hours and should not be attributable to confounding clinical factors (e.g. fever, infection, injury, adverse reactions to concomitant medications). When a patient experiences new or worsening symptoms that may indicate a possible relapse, he/she should telephone the treating investigator within 48 hours of symptoms onset. The treating investigator, study nurse, or other medically qualified individual will conduct a telephone questionnaire and, as necessary, will arrange an unscheduled relapse assessment visit.

## 11.1.4. Multiple Sclerosis Functional Composite (MSFC)

The MSFC (Cutter, 1999) is a battery of the following 3 individual scales:

- The Timed 25-Foot Walk is a quantitative measure of lower extremity function
- The 9-Hole Peg Test is a quantitative measure of upper extremity (arm and hand) function
- The PASAT-3 is a measure of executive function cognition that specifically assesses auditory information, processing speed, and flexibility, as well as calculation ability

The same person, either the blinded evaluator or another independent designated team member trained in conducting MSFC assessments should administer the 3 scales that make up the MSFC with each participating patient throughout the study.

The MSFC z-score is calculated by creating z-scores for each component of the MSFC, as explained below, and averaging them to create an overall composite score, i.e.,

MSFC z-score = (Z25-foot-walk + Z9HPT + ZPASAT3)/3, where Zxxx refers to Z-scores

Details on the calculations of the z-score for each component will be described in the statistical analysis plan (SAP).

#### 11.1.5. Low-Contrast Letter Acuity Test (LCLA)

The LCLA, which is performed with the MSFC assessments, is performed with a standardized set of charts (e.g. Sloan letter charts or Tumbling E charts) to assess low contrast visual acuity. Each chart corresponds to a different contrast level, and charts are scored according to the number of letters that are identified correctly. The LCLA captures aspects of neurological dysfunction that is not assessed by the EDSS or MSFC, and has been proposed as an additional component to the MSFC (Balcer, 2003).

#### 11.1.6. Multiple Sclerosis Quality of Life-54 (MSQOL-54)

The MSQOL-54 is a multidimensional health-related quality of life measure that combines both generic and MS-specific items into a single instrument (Vickrey, 1995). This 54-item instrument generates 12 subscales along with two summary scores, and two additional single-item measures. The subscales are: physical function, role limitations-physical, role limitations-emotional, pain, emotional well-being, energy, health perceptions, social function, cognitive function, health distress, overall quality of life, and sexual function. The summary scores are the physical health composite summary and the mental health composite summary. The single item measures are satisfaction with sexual function and change in health.

The MSQOL-54 is a structured, self-report questionnaire that the patient can generally complete with little or no assistance. It may also be administered by an interviewer. However, patients with visual or upper extremity impairments may need to have the MSQOL-54 administered as an interview by the study nurse (or study coordinator). Interviewers should be trained in basic interviewing skills and in the use of this instrument.

# 11.2. Safety Assessments

#### 11.2.1. Clinical Safety Assessments

#### **Physical Examination**

A complete physical examination will include evaluation of heart, lung, head and neck, abdominal, skin, and extremities. The EDSS, performed by the blinded evaluator, serves as the neurological examination. An interim (or brief) physical examination will include areas with previously noted abnormalities and/or that are associated with any new complaints from the patient.

Initial neurological examination will be a part of the physical examination at screening and if warranted by an unscheduled visit. All significant findings that are present at screening must be reported on the relevant medical history/current medical conditions eCRF. Significant findings made after randomization that meet the definition of an AE must be recorded on the AEs eCRF.

#### **Height and Weight**

Height will be measured at screening in Part A and Part B and at the end of the study.

Weight will be measured at screening, Baseline (Day 1), Week 24 and end of study or early termination in Part A and screening, Baseline (Day 1), Month 12, and Month 24 or early termination in Part B.

#### **Vital Signs**

Blood pressure, heart rate and body temperature will be assessed.

For the Baseline (Day 1) visit and during dose titration (Day 5 and Day 8, as applicable), vital signs should be recorded after the patient has been supine for 10-15 minutes, systolic and diastolic blood pressure and heart rate will be measured 3 times using an automated validated device. The repeat measurements will be made at 2-minute intervals and the lowest of the 3 measurements will be recorded on the eCRF, based on systolic BP. For all other visits, vital signs will be assessed once and recorded on the eCRF.

In case the cuff sizes available are not large enough for the patient's arm circumference, a sphygmomanometer with an appropriately sized cuff may be used. Orthostatic blood pressure will then be measured once with the patient in the standing position (after standing for 2 minutes). A sudden, significant fall in blood pressure (>20 mmHg) between 2 and 5 minutes after standing from the supine position will be interpreted as an orthostatic hypotension and will be documented in the patient chart and eCRF.

Patients will be carefully monitored after the first dose of study medication with a 6 hour post-dose monitoring period of hourly recording of orthostatic blood pressure.

#### **Chest X-ray**

To be performed only at screening of Part A and Part B. It is not required if performed within 60 days prior to randomization and if documentation is on file.

#### **ECG**

12-lead ECG to be performed after the patient has been resting quietly for at least 10-15 minutes.

Digital ECG devices will be provided to each clinical site by the central ECG laboratory for the duration of the study. The screening ECG report from the central reader must be available to confirm patient eligibility before randomization. A 12-lead ECG will be performed before and 6 hours after the first dose of study drug administration, while the patient is at the clinic.

Detailed instructions describing the process for recording and transmission of the digital ECGs will be outlined in the study-specific manual and provided to the site before the start of the study. Stand-alone ECGs will be obtained, printed, photocopied to preserve the ink if necessary, and kept at the site as source documentation.

#### ECG & Holter Monitoring

Dual function Digital ECG devices that are capable of capturing both stand-alone ECGs and Holter data will be provided to each clinical site by the central ECG laboratory for the duration of the study. Detailed instructions describing the process for recording and transmission of the digital ECGs and Holter data will be outlined in the study-specific manual and provided to the site before the start of the study.

#### Stand Alone/Static ECGs

Static ECGs will be captured at intervals as defined in the schedule of assessments (Section 9.1.1). The 12-lead ECG will be performed after the patient has been resting quietly in a supine position for at least 10-15 minutes. The screening 12-lead ECG report from a central reader must be available to confirm patient eligibility before randomization. 12-lead ECGs will be performed before and 6 hours after the first dose of study drug administration for all patients on Day 1 and for the first 75 patients at Day 5, while the patient is in the clinic. Six hour post dose ECG will be evaluated by treating neurologist, with input if needed from a local cardiologist or a central reader to confirm if extended monitoring is required. Simultaneously the ECGs will be printed out locally, photocopied to preserve the ink if necessary, and kept at the site as source documentation.

Each ECG tracing should be labeled with the study number, patient initials, patient number, date, and kept in the source documents at the study site. Only clinically significant abnormalities should be reported in the medical history/current medical conditions or adverse event CRF. Clinically significant findings must be discussed with the Medical Monitor before enrolling the patient in the study.

#### Continuous 12-lead Holter Monitoring

24 hour continuous cardiac monitoring (12 lead digital Holter monitoring) will be captured for all Part A patients at Day 1 and the first 75 patients at Day 5 and Day 8. Holter monitoring will start at least 15 minutes prior to dose and complete at least 24 hours post dose administration. Patient should be in the supine position prior to Holter application through the capture of the static pre-dose 12-lead ECG as well as for the acquisition of the 6 hour post dose 12-lead ECG. Holter analysis parameters will be described in the operations document.

#### **Pulmonary Function Tests**

Pulmonary function tests including FEV1 and FVC measurements will be performed as scheduled Table 1 and Table 2 (Part A), and Table 3 and Table 4 (Part B). In addition, DLCO will be performed at screening and at the Week 24 visit of Part A and at Month 12 and Month 24 for Part B. With prior approval from the sponsor, DLCO will not be required at sites where there is no local DLCO testing facility available. In addition to scheduled assessments, the pulmonary function tests should also be performed as clinically indicated in the event of clinically significant pulmonary signs or symptoms. These tests will be performed at a high quality pulmonary function testing center with the appropriate certification (as locally required), and will be overseen by a pulmonologist who does not need to see the patients. If any PFT abnormalities occur, they will be followed until such time as resolution is confirmed or no further improvement is expected by the investigator (based on a follow-up period of not less than 3 months). Patients who discontinue due to respiratory AEs should be evaluated by a pulmonary specialist and further investigations (pulmonary function test, chest radiography, high resolution chest tomography or biopsy) should be performed as needed.

The technician should demonstrate the appropriate spirometry technique to the patient and follow the standard procedure. The quality of the tests must be accounted for including the technicians' comments (especially when, despite proper coaching of the patient, full collaboration cannot be achieved). A central trial statistician will calculate the FEV1/FVC ratio.

A minimum of 3 acceptable maneuvers will be performed at each visit. The acceptability criteria are a satisfactory start of test and a satisfactory end of test. In addition, the technician should observe that the patient understood the instructions and performed the maneuver with a maximum inspiration, a good start, a smooth continuous exhalation, and maximal effort. The largest FVC and the largest FEV1 will be recorded, after examining the data from all of the acceptable curves, even if the 2 values do not come from the same curve. Please refer to the American Thoracic Society/European Respiratory Society guidelines for standardization of spirometry and single breath determination of carbon monoxide uptake in the lung (MacIntyre, 2005; Miller, 2005a; Miller, 2005b).

If for any reason a patient is permanently discontinued from study medication the patient will have the pulmonary function tests performed at his last visit or within 30 days of the study drug discontinuation.

Two acceptable DLCO tests should be performed at each scheduled timepoint. A DLCO test is acceptable if it fulfills all the following criteria:

- Use of proper quality-controlled equipment
- Inspired volume of greater than 85% of largest vital capacity in less than 4 seconds

- A stable calculated breath hold for 10 (±2) seconds. There should be no evidence of leaks or Valsalva or Mueller maneuvers
- Expiration in less than 4 seconds (and sample collection time less than 3 seconds), with appropriate clearance of dead space and proper sampling/analysis of alveolar gas.
- All values must be corrected for hemoglobin concentration in the study, using the central laboratory haemoglobin value for the respective visit.

#### **Ophthalmological Examination**

OCT will be performed as scheduled in Table 1 and Table 2 (Part A), and Table 3 and Table 4 (Part B). If there is a suspicion of macular edema, then general retinal exams including eye history, visual acuity, and dilated ophthalmoscopy will be obtained. A general ophthalmologist can do the examination, although a retinal specialist would be preferred to do the exams wherever possible.

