All safety data will be listed and summarized by treatment group. All treatment-emergent AEs will be coded and tabulated by system organ class and preferred term. Incidence of AEs, SAEs, and AEs leading to discontinuation will be summarized and presented in descending order of frequency. Associated laboratory parameters such as hepatic enzymes, renal function, and hematology values will be grouped and presented together. Individual patient values will be listed and values outside of the standard reference range will be flagged. Shift tables and analyses of changes from Baseline will be produced. The change from Baseline for each of the vital signs and ECG parameters will be summarized. Incidence of abnormal vital signs parameters and outlier ECG results will be tabulated.

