## Part A and Part B

Safety and tolerability will be evaluated in this study by the incidence and type of AEs, SAEs, AEs leading to discontinuation of study treatment, the incidence and type of laboratory abnormalities, vital sign, ECG, and physical exam abnormalities in all patients. In addition, descriptive characterization of target AEs of interest including bradycardia and heart conduction abnormalities (ECG, vital signs, continuous Holter monitoring [Part A only]), pulmonary toxicity (FEV1, FVC measurements), and lung diffusion capacity testing [DLCO] measurements), macular edema (optical coherence tomography [OCT]), hepatotoxicity (LFTs), cutaneous malignancy (dermatological exams), and suicidality (Columbia- Suicide Severity Rating Scale [C-SSRS]) will occur in both Part A and Part B of the study.

Safety assessments will include the following:

- AEs
- Laboratory evaluations
- Vital sign measurements
- ECG results
- Continuous Holter monitoring
- Physical and neurological examination
- OCT
- Pulmonary function tests
- Dermatological examination
- Columbia-Suicide Severity Rating Scale (C-SSRS)

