#### 10.3.10. Visit 10 (Month 24/Week 104 $\pm$ 5 days)

Patients are expected to remain in Part B for 24 months.

The following assessments will be performed at Visit 10 (Month 24):

- Blood/urine sampling for the following laboratory tests:
  - Hematology: RBC count, total and differential WBC count (basophils, eosinophils, lymphocytes, monocytes, and neutrophils), platelet count, hemoglobin, hematocrit, MCV, MCH, and MCHC
     Note: All total WBC and differential WBC counts will be blinded during the study.
  - Blood chemistry: sodium, potassium, chloride, calcium, magnesium, phosphate, blood urea nitrogen, random glucose, albumin, alkaline phosphatase, creatinine, SGPT/ALT, SGOT/AST, GGT, amylase, total bilirubin, conjugated bilirubin, hemoglobin A1c, and total cholesterol, triglycerides, HDL and LDL. Abnormal laboratory parameters inconsistent with clinical presentation of MS or suspicious of underlying medical condition should be repeated for accuracy. If an increase of amylase above the clinically notable value (≥ 300 U/L) is observed at any post randomization visit, lipase should be tested to determine the origin of elevated amylase (pancreatic versus extra pancreatic)
  - Urinalysis: leukocytes, specific gravity, bilirubin, blood, glucose, ketones, pH, protein, and urobilinogen
  - Urine beta-hCG (females of childbearing potential only). If the urine pregnancy test is positive, do not dose and confirm with a serum pregnancy test.
  - Coagulation panel: PT and PTT
  - sTSH

- Standard PK sampling: PK samples are to be taken 2 to 6 hours following administration
- Complete physical examination: including evaluation of heart, lung, head and neck, abdominal, neurological, skin, and extremities
- Weight
- Vital signs: body temperature, blood pressure and heart rate
- 12-lead ECG
- If patients will continue on treatment, dispense study drug and patient diary
- Review study drug accountability and compliance
- Brain MRI
- EDSS and neurological examination
- MSFC AND LCLA
- MSQOL-54
- Pulmonary function tests including FEV1 and FVC measurements, and DLCO
- OCT evaluation
- Dermatological examination
- Suicidality assessment using the C-SSRS
- Record concomitant therapy
- Record AEs/SAEs

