## Monitoring of Patients with Adverse Events of Special Interest

Several of the AEs noted in fingolimod clinical studies may be a consequence of S1P1R stimulation and will therefore be closely monitored in the RPC01-201 study. These AEs include:

- a. Bradycardia and heart conduction abnormalities. Dose-related transient, reversible bradycardia, symptomatic bradycardia, and first, second, or higher degree atrioventricular block were reported primarily as first dose effects in fingolimod studies. The heart rate reduction observed with sphingosine-1-receptor agonists is an expected effect of S1PR modulation and appears to be conducted through the same pathway as vagus nerve stimulation. In addition, these negative chronotropic effects of S1P1R agonists appear to attenuate over time secondary to S1PR desensitization and internalization on cardiac myocytes (Kovarik 2008). This effect appears to occur with increasing exposures of study drug, thus gradual titration of the dose of RPC1063 over several days may mitigate against larger reductions in HR.
- b. Pulmonary toxicity. An initial sharp decrease followed by a slow progressive decline over time in FEV1 was observed in fingolimod clinical studies. Nonclinical toxicity studies with RPC1063 have revealed the potential for pulmonary toxicity at doses considerably higher than the pharmacologically active dose. FEV1, FVC, and DLCO will be measured in all patients. Every patient whose PFTs are abnormal will be followed until such time as resolution is confirmed or no further improvement is expected by the investigator (based on a follow-up period of not less than 3 months).
- c. Hepatotoxicity. Fingolimod caused frequent, reversible liver enzyme elevations greater than 3-fold above the upper limit of normal in up to 12% of patients; this was a significant cause of cessation of therapy. In this study, clinical chemistry analyses to assess LFTs will be performed. Every patient whose LFTs are abnormal will be followed until values return to baseline.
- d. Macular edema. Instances of serious macular edema were reported in fingolimod renal transplant studies, and a 0.8% incidence was reported as an SAE in fingolimod (1.25 mg dose) MS clinical studies. Nonclinical studies with RPC1063 have not revealed eye-related toxicities. In this study, measurement of central foveal thickness by OCT will be performed in all patients. For patients

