### 10. SAFETY ANALYSIS

All analysis of safety will be conducted using the Safety population. Statistical hypothesis testing will not be performed on any safety results. No imputation of missing safety data will be performed.

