#### **10.1.7.** Adverse Events of Special Interest

Target AEs of special interest will be closely monitored in the study. These AEs include infections, malignancies, cardiac (bradycardia and heart conduction abnormalities), pulmonary function (decline in FEV1, FVC, and DLCO measurements), ophthalmic (macular edema), hepatic (LFT elevations), and dermatological (cutaneous malignancy) abnormalities. These AEs will be summarized in tables and presented in a listing.

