## 10.9. Other Assessments

A summary table of dermatological abnormalities by visit will be presented. Listings of dermatological abnormalities and abnormalities in optical coherence tomography (OCT) assessment will be provided.

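### Part B: foveal thickness is measured by OCT in every patient, but the SAP only lists OCT abnormalities, so thickness, its change and abnormal-OCT counts have no by-arm summary

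*Protocol*

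**What the plan says.** **Measurement.** Protocol 11.2.1 (Ophthalmological Examination) refers to the schedules: "OCT will be performed as scheduled in Table 1 and Table 2 (Part A), and Table 3 and Table 4 (Part B". Protocol 12.4 says what is measured and in whom: "measurement of central foveal thickness by OCT will be performed in all patients". In Part B, Table 3 puts OCT at screening and Months 6, 12 and 24, and Table 4 adds early termination. The Month 24 visit text, for example, lists "OCT evaluation". An abnormal OCT, or visual signs or symptoms, triggers a fuller eye examination.

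**Commitment to summarize.** Protocol 8.2.2 promises a descriptive account of target adverse events in both parts, including "macular edema (optical coherence tomography [OCT"). The synopsis, under the Part B statistical methods, is broader: "All safety data will be listed and summarized by treatment group".

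**Planned output.** SAP 10.9 is the only SAP section that handles OCT results: "Listings of dermatological abnormalities and abnormalities in optical coherence tomography (OCT) assessment will be provided". The sentence before it gives skin findings a by-visit summary table; OCT has no counterpart. Macular edema as an adverse event of special interest is covered in SAP 10.1.7: "These AEs will be summarized in tables and presented in a listing". SAP 10 adds: "Statistical hypothesis testing will not be performed on any safety results".

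**Scope.** SAP Section 2 limits the SAP to Part B. Part A has its own plan, which is not among the documents.

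**The concern.** A continuous retinal measurement is taken repeatedly in about 1200 patients because the drug class is associated with macular edema, which the protocol treats as an event of special interest. The planned output from those measurements is a patient-level listing, restricted to results called abnormal. Neither document defines an abnormal OCT, so the listing has no stated inclusion rule.

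Two things therefore have no arm-level result: any shift in average thickness, and the number of patients whose OCT was abnormal but was not recorded as an adverse event. If diagnosed cases are few, these are the data that could show whether the RPC1063 arms differ from interferon, or from each other, short of a diagnosis. Only safety description is at stake; no efficacy conclusion depends on it.

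**Working it through.** **1. Denominator.** The documents state no expected number of macular edema cases, so the only plan figure to reproduce is the number per arm. With n per arm = φ × (1/r1 + 1/r2)/t × (z for two-sided 0.025 + z for power)² / ln(r2/r1)²:

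- Protocol 13.2 (φ = 1.3, rates 0.30 and 0.19, t = 2 years, 90% power): 332.4, so 333, as stated. Then 333/(1 − 0.17) gives 402, against about 400 planned.
- SAP 5.1 (φ = 1.3, rates 0.30 and 0.17, t = 1 year, 80% power): 352.98, so 353, as stated. Then 353/(1 − 0.12) gives 402, again about 400.

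So 333 to 400 per arm is a fair range for patients contributing OCT data.

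**2. How the SAP treats comparable safety measurements.**

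| Measurement | SAP output |
|---|---|
| Skin examination (10.9) | By-visit summary table and listing |
| FEV1 and FVC (10.5) | Actual value, change, percent change, percent predicted; line plots |
| ALT, AST, GGT (10.2.2) | By-arm, by-visit counts above multiples of the upper limit of normal |
| OCT (10.9) | Listing of abnormalities only |

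All four serve adverse events of special interest named in SAP 10.1.7. OCT alone has no summary table, and no reason is given.

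**3. What already reaches an arm-level view.**

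- SAP Section 5 orders every listing by treatment group, so abnormal OCTs can be counted by hand from the listing.
- Protocol 12.7 has clinically significant safety findings recorded as adverse events, at the investigator's judgment.
- Macular edema recorded as an adverse event enters the incidence tables (SAP 10.1.1) and the special-interest tables (10.1.7). Because Protocol 9.4.4.1 and 12.4 link a new or worsened diagnosis to discontinuation, it also enters the table of events leading to discontinuation (10.1.5).

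What remains without a by-arm summary is mean thickness, change from Baseline, and a tabulated count of abnormal OCTs not recorded as adverse events.

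**4. How sparse diagnoses might be.** Protocol 12.4 quotes one MS incidence, 0.8%, for events reported as serious with fingolimod 1.25 mg. Carrying it to an RPC1063 arm is an assumption.

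- Expected cases: 400 × 0.008 = 3.2 (353 × 0.008 = 2.8; 333 × 0.008 = 2.7).
- Both RPC1063 arms together: 800 × 0.008 = 6.4.
- Range: 400 × 0.002 = 0.8 to 400 × 0.016 = 6.4 per arm.
- Chance of no case in an arm of 400: 0.992^400 = 4.0% at 0.8%; 44.9% at 0.2%; 0.16% at 1.6%.
- Exact 95% intervals: 3/400 gives 0.15% to 2.18%; 0/400 gives an upper limit of 0.92%, so a true 0.8% could not be excluded.

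**5. Precision of the missing summary.** With a common SD and every counted patient measured, the 95% CI half-width for a difference in mean change between two arms is 1.96 × √(2/n) SD: 0.14 SD at n = 400 and 0.15 SD at n = 333. The documents give no SD for thickness, so this cannot be put in microns.

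**The case against.** The strongest reply is that this is a presentation matter. The OCT listing is ordered by arm, so an excess of abnormal scans is not hidden. The adverse event route is wider than a diagnosis of macular edema, since Protocol 12.7 also brings in other changes judged clinically significant. A reader might infer from SAP 10.9 that the plan has no by-arm macular evidence beyond one special-interest count; step 3 of the check shows that this is not so.

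The promise in Protocol 8.2.2 can also be overread. Its object is the adverse event, with OCT in brackets as the means of detection; the matching synopsis text names ophthalmic exams instead. It does not by itself commit to a thickness analysis. The synopsis sentence on all safety data is better support, but it is general, and Protocol 13.6.6 speaks only of adverse events.

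A reader might also take three cases per arm as the trial's forecast. It is not one. The 0.8% belongs to another drug, at one dose, for events reported as serious; all diagnoses could be more frequent, and no rate is given for interferon. Nor would it help to argue from the power of a test on these counts or on thickness, because the SAP rules out safety testing.

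Finally, the documents do not show that numeric thickness is recorded in the case report form, or whether scans are read locally or centrally.

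All of this stands and limits the point. It does not supply the missing summary: an arm-sorted listing of abnormal results gives neither mean thickness nor change from Baseline, nor a count with its denominator, and it falls short of the synopsis commitment.

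**Conclusion.** The point holds in a limited form, for Part B only. A measurement required in every patient has no by-arm summary, although the synopsis says safety data will be summarized by arm and the SAP does this for skin, pulmonary and liver assessments. The gap covers mean thickness, change from Baseline, and tabulated counts of abnormal OCTs not recorded as adverse events.

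The case for closing it rests on diagnoses probably being few: 3.2 per RPC1063 arm of 400 if the borrowed 0.8% applied, and 0.8 to 6.4 for assumed rates of 0.2% to 1.6%. Those figures are conditional.

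Because Part B admits patients with controlled type 2 diabetes and Protocol 9.4.3.1 asks for close macular monitoring of them, a reader might infer that a separate by-arm diabetes analysis is owed. That section is an instruction to sites, it excludes patients with diabetic retinopathy, and no expected number of such patients is given. A listing or simple counts would be enough.

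This is an inexpensive improvement to safety reporting. It is not a flaw in the design or the efficacy analysis.

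**What to change.** First confirm that numeric central foveal thickness is captured in the database. Then add to SAP 10.9, as description only:

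- **Thickness table:** central foveal thickness and change from Baseline, by arm and visit, with 95% CIs. The screening OCT serves as Baseline under SAP 5.4.1.
- **Abnormality table:** by arm and visit, the number and percentage of patients with an abnormal OCT, under a definition written into the SAP before unblinding, and the number with a triggered ophthalmologic examination. State that the denominator is patients with an OCT at that visit; otherwise the SAP Section 5 default, all patients in the arm, would apply, and SAP 10 allows no imputation of missing safety data.
- **Type 2 diabetes:** a flag in the existing listing, or simple counts.

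If numeric values are not captured, the abnormality table can still be produced.

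The cost is one or two table shells, a written definition and the check on data capture. Readings may be noisy if devices or readers differ between sites; using change within patient limits this. No visits, hypothesis tests or changes to patient management are added.
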